10.3.2.3 Assessment of Potentially Clinical Significant Laboratory Values

The criteria for potentially clinically significant laboratory values will be determined by CTCAE criteria of Grade 3 or higher. The number and percentage of subjects meeting the criteria for potentially clinically significant laboratory values will be summarized by "as treated" treatment group.

10.3.2.4 Assessment of Liver Elevations

According to FDA's Guidance for Industry "Drug-Induced Liver Injury: Premarketing clinical evaluation" (July 2009), when aminotransferase (AT) abnormalities indicating hepatocellular injury are accompanied by evidence of impaired hepatic function (bilirubin elevation $> 2 \times \text{ULN}$), in the absence of evidence of biliary obstruction (i.e., significant elevation of ALP) or some other explanation of the injury (e.g., viral hepatitis, alcohol hepatitis), the combined finding (i.e., Hy's Law cases) represents a signal of a potential for the drug to cause severe DILI.

For the purpose of assessing for potential Hy's law cases, the frequencies and percentages of subjects with post baseline liver specific function test values that meet the following criteria of potential clinical interest will be summarized by "as treated" treatment group:

- $\text{ALT} \geq 3 \times \text{ULN}$
- $\text{ALT} \geq 5 \times \text{ULN}$
- $\text{ALT} \geq 10 \times \text{ULN}$
- $\text{ALT} \geq 20 \times \text{ULN}$
- $\text{AST} \geq 3 \times \text{ULN}$
- $\text{AST} \geq 5 \times \text{ULN}$
- $\text{AST} \geq 10 \times \text{ULN}$
- $\text{AST} \geq 20 \times \text{ULN}$
- $\text{TBL} \geq 2 \times \text{ULN}$

- Alkaline phosphatase $\geq 1.5 \times \text{ULN}$
- ALT and/or AST $\geq 3 \times \text{ULN}$ and concurrent TBL $\geq 1.5 \times \text{ULN}$
- ALT and/or AST $\geq 3 \times \text{ULN}$ and concurrent TBL $\geq 2 \times \text{ULN}$

10.3.3 Analysis of Long-Term Laboratory Data

10.3.3.1 Assessment of Mean Change from Baseline and Percentage Change from Baseline in Clinical Laboratory Variables

Analyses of specified continuous hematology, chemistry, and urinalysis variables which are measured longitudinally will be performed by visits and by "as treated" treatment group sequences as described in Section 10.1. For each parameter, the following summary statistics will be presented for each treatment group sequence: sample size, mean, standard deviation, minimum, median and maximum.

Analyses will be performed for change and percentage change from baseline in hemoglobin, lymphocytes, neutrophils, creatinine, creatine phosphokinase (CPK), LDL, HDL, the ratio of LDL to HDL, and total cholesterol.

10.3.3.2 Assessment of Potentially Clinical Significant Laboratory Values

Long-term laboratory data will also be summarized based on the number and percentage of subjects meeting the criteria for potentially clinical significant laboratory values for the Any Upadacitinib 15 mg QD group as described in Section 10.2.2.

The baseline value will be determined by the last non-missing measurement recorded on or before the date of the first dose of Upadacitinib 15 mg QD. For a subject who started on placebo and switched to upadacitinib 15 mg QD at Week 14, lab values under upadacitinib 15 mg QD exposure would be evaluated against the baseline value defined as above.

A listing of all subjects with any laboratory determination meeting CTCAE criteria of Grade 3 or higher will be provided by grade. For each of these subjects, the whole course of the respective parameter will be listed.

10.3.3.3 Assessment of Liver Elevations

The frequencies and percentages of subjects with post-baseline liver-specific function test values that meet the following criteria of potential clinical interest will be summarized for Any Upadacitinib 15 mg QD group as described in Section 10.2.2:

- $ALT \geq 3 \times ULN$
- $ALT \geq 5 \times ULN$
- $ALT \geq 10 \times ULN$
- $ALT \geq 20 \times ULN$
- $AST \geq 3 \times ULN$
- $AST \geq 5 \times ULN$
- $AST \geq 10 \times ULN$
- $AST \geq 20 \times ULN$
- $TBL \geq 2 \times ULN$
- Alkaline phosphatase $\geq 1.5 \times ULN$
- ALT and/or $AST \geq 3 \times ULN$ and concurrent $TBL \geq 1.5 \times ULN$
- ALT and/or $AST \geq 3 \times ULN$ and concurrent $TBL \geq 2 \times ULN$

A listing of potentially clinically significant liver elevations based on criteria specified above will be provided. For each of these subjects, the whole course of the respective parameter will be listed.

10.4 Analysis of Vital Signs

10.4.1 Variables and Criteria Defining Abnormality

Vital sign variables include sitting systolic blood pressure, sitting diastolic blood pressure, pulse rate, respiratory rate, body temperature, and weight. The criteria for potentially clinically significant vital sign findings are presented in [Table 11](#).

Table 11. Criteria for Potentially Clinically Significant Vital Sign Findings

Vital Sign	Category	Criteria for Potential Clinically Significant Vital Signs
Systolic blood pressure	Low	Value \leq 90 mmHg and decrease \geq 20 mmHg from Baseline
	High	Value \geq 160 mmHg and increase \geq 20 mmHg from Baseline
Diastolic blood pressure	Low	Value \leq 50 mmHg and decrease \geq 15 mmHg from Baseline
	High	Value \geq 105 mmHg and increase \geq 15 mmHg from Baseline
Pulse	Low	Value \leq 50 bpm and decrease \geq 15 bpm from Baseline
	High	Value \geq 120 bpm and increase \geq 15 bpm from Baseline
Respiratory Rate	Low	< 10 rpm
	High	> 24 rpm
Body temperature	High	> 39.0°C (102.3°F)
Weight	High	> 7% increase from baseline
	Low	> 7% decrease from baseline

10.4.2 Analysis of Vital Sign for Period 1

Analyses of continuous vital sign variables which are measured longitudinally will be performed by visits and by the treatment groups of Upadacitinib 15 mg QD and placebo group. For each analysis, the following summary statistics will be presented for each treatment group: sample size, mean, standard deviation, minimum, median and maximum. The number and percentage of subjects meeting the criteria for potentially clinically significant vital sign values will be summarized by "as treated" treatment group.

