8.1.5 Safety Analysis

8.1.5.1 General Considerations

Safety analyses will be carried out using the Safety Analysis Set. Analyses will be conducted in primary analysis at Week 14, as well as for the entire study.

Safety analyses are based on treatments actually received. Safety will be assessed by treatment-emergent adverse events (TEAEs), physical examination, laboratory assessments, and vital signs. The number and percent of subjects experiencing TEAEs by treatment group will be tabulated by the Medical Dictionary for Drug Regulatory Activities (MedDRA[®]) system organ class (SOC) and preferred terms (PT). In addition,

summary of serious AEs and TEAEs by severity and relationship to study drug as assessed by the Investigators will be provided. SAEs, severe TEAEs, or TEAEs that lead to premature study discontinuation will be listed. The changes in vital signs, physical examination results, and clinical laboratory variables at each visit as compared to baseline will be summarized. Shift of laboratory values from baseline at defined time points will be tabulated.

Missing safety data will not be imputed.

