8.1.5.3 Analysis of Laboratory and Vital Sign Data

Changes from baseline by visit; changes from baseline to minimum value, maximum value, and final values in continuous laboratory data; and vital signs will be summarized by treatment group.

Baseline values are defined as the last non-missing measurements recorded on or before the date of the first dose of study drug.

The laboratory data will be categorized as Grade 1, Grade 2, Grade 3, Grade 4, or Grade 5 according to CTCAE criteria. The shift tables will tabulate the number and percentage of subjects with baseline and post-baseline values by grade levels.

Summary and listings will be provided for potentially clinically significant laboratory values and vital signs.

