10.3 Analysis of Laboratory Data

10.3.1 Variables and Units

All laboratory parameters to be collected in this study are listed below. Laboratory parameters will be reported using the standard international (SI) units.

Table 10. List of Laboratory Variables

Laboratory Variables
Hematology
White Blood Cell (WBC) Count
Red Blood Cell (RBC) Count
Hemoglobin
Hematocrit
Platelets count
Neutrophils
Basophils
Eosinophils
Lymphocytes
Monocytes
Bands
Chemistry
Total Bilirubin
Alkaline Phosphatase (ALP)
Aspartate aminotransferase (AST)
Alanine aminotransferase (ALT)
Total Protein
Albumin
Glucose
Triglycerides
Blood Urea Nitrogen (BUN)
Creatinine
Uric acid
Sodium
Potassium
Calcium
Inorganic Phosphorus
Creatine Phosphokinase (CPK)
Chloride
Bicarbonate

Table 10. List of Laboratory Variables (Continued)

Laboratory Variables
Chemistry (Continued)
Cholesterol
LDL cholesterol
HDL cholesterol
LDL/HDL ratio
Cholesterol/HDL ratio
Urinalysis
Specific Gravity
pH
Protein
Glucose
Ketones
Blood
Microscopic Examination (if needed)
Urobilinogen
Bilirubin
Leukocytes
Nitrites
Other
hs-CRP
QuantiFERON-TB Gold ^a
ESR

a. For annual follow-up QFT is captured only for those with negative QFT at Screening.

10.3.2 Analysis of Laboratory Data for Period 1

The laboratory data will be summarized by the "as treated" treatment groups (Upadacitinib 15 mg QD and placebo group).

10.3.2.1 Assessment of Mean Change from Baseline and Percentage Change from Baseline in Clinical Laboratory Variables

Analyses of continuous hematology, chemistry, and urinalysis variables which are measured longitudinally will be performed by visits and by treatment group. For each parameter at each visit, the following summary statistics will be presented for each treatment group: sample size, mean, standard deviation, minimum, median and maximum.

An ANOVA model with treatment as a factor will be used to compare change and percent change from baseline between different treatment groups for selected laboratory parameters. Mean difference from placebo and associated 95% CIs will be presented. The analysis applies to the following laboratory parameters of clinical interest: hemoglobin, platelets, lymphocytes, neutrophils, creatinine, creatine phosphokinase (CPK), LDL, HDL, the ratio of LDL to HDL, and total cholesterol.

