10.4.3 Analysis of Long-Term Vital Sign

Analyses of mean change from baseline in continuous vital signs variables which are measured longitudinally will be performed by visits and by "as treated" treatment group sequences as described in Section 10.1. For each change from baseline analysis, the following summary statistics will be presented for each treatment group: sample size, baseline mean, visit mean, and the mean, standard deviation, and median of the changes from baseline.

Long-Term Vital Sign will also be summarized based on the number and percentage of subjects meeting the criteria for potentially clinical significant vital sign values for the Any Upadacitinib 15 mg QD group as described in Section 10.2.2. Similar baseline definition as described in Section 10.3.3.2 will be applied.

A listing of all subjects with any vital sign values meeting the criteria for potentially clinically significant vital signs will be provided. For each of these subjects, the whole course of the respective parameter will be listed.

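### SAP 10.4.2 does not specify the Period 1 change-from-baseline summary of vital signs that the protocol promises for the Week 14 analysis

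*SAP*

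**What the plan says.** **Protocol.** Section 8.1.5.1 states: "The changes in vital signs, physical examination results, and clinical laboratory variables at each visit as compared to baseline will be summarized". The synopsis says the same. The same section says the safety analyses are "conducted in primary analysis at Week 14, as well as for the entire study", so the commitment covers the placebo-controlled data. Section 8.1.5.3 lists the summaries by treatment group: "Changes from baseline by visit; changes from baseline to minimum value, maximum value, and final values in continuous laboratory data; and vital signs". Its punctuation leaves some doubt about how far the change wording reaches vital signs, but 8.1.5.1 leaves none.

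**SAP, Period 1.** Section 10.4.2 reads: "Analyses of continuous vital sign variables which are measured longitudinally will be performed by visits and by the treatment groups", and then: "For each analysis, the following summary statistics will be presented for each treatment group: sample size, mean, standard deviation, minimum, median and maximum". The Period 1 text of 10.1 also speaks only of the variables at each visit. In addition, 10.4.2 gives counts by arm of subjects meeting the Table 11 criteria for potentially clinically significant values.

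**SAP, elsewhere.** Section 10.4.3, for long-term data, begins: "Analyses of mean change from baseline in continuous vital signs variables which are measured longitudinally will be performed by visits". It lists n, the baseline and visit means, and the mean, SD and median of the change. For Period 1 laboratory data, 10.3.2.1 has change from baseline in its heading and adds: "An ANOVA model with treatment as a factor will be used to compare change and percent change from baseline", with mean differences from placebo and 95% CIs for selected parameters.

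**The concern.** Safety and tolerability in Period 1 is one of the trial's primary objectives. Period 1 is also the only time the arms differ in treatment, because at Week 14 the placebo subjects who continue start upadacitinib. A moderate drug effect on weight, blood pressure or pulse therefore has to be judged from the Baseline to Week 14 data.

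For that period the SAP specifies means and SDs of the variables at each visit. If these are visit values, their SDs carry the full spread between subjects, and a comparison of arms at a visit carries any chance imbalance at baseline. Neither the SD of the change nor a between-arm difference is specified.

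The Table 11 counts do not fill the gap, because they are built for large individual excursions. Weight must move by more than 7%. High systolic pressure needs a value of at least 160 mmHg together with a rise of at least 20 mmHg, so a rise from 120 to 155 mmHg (35 mmHg) is not counted.

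**Working it through.** **1. The texts side by side**

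| Place | Data | Change from baseline named? | Between-arm difference? |
|---|---|---|---|
| Protocol 8.1.5.1 | Vital signs and laboratory; Week 14 and whole study | Yes, by visit | No |
| SAP 10.1 and 10.4.2 | Vital signs, Period 1 | No | No |
| SAP 10.4.3 | Vital signs, long term | Yes, by visit and treatment sequence | No |
| SAP 10.3.2.1 | Laboratory, Period 1 | Yes | Yes, selected parameters, 95% CI |

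Sections 10.4.2 and 10.4.3 sit close together and use different lists of statistics. Only the second contains the baseline mean and the statistics of the change. That contrast supports reading 10.4.2 as an omission.

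**2. The anchor for sample size**

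The plan gives no precision figure for vital signs. Its one related figure is N = 170 (protocol 8.2, SAP 4.3). For 20% against 46%, two-sided 0.05 and 90% power, the continuity-corrected formula gives 75 per arm. Allowing for 10% dropout, 75 / 0.9 = 83.3, so 84 per arm or 168 in total, which agrees with 170. I therefore use n = 85 per arm.

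**3. Precision of a between-arm comparison at one visit**

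Assumptions, none of them in the documents: weight SD 16 kg with baseline-to-visit correlation ρ of 0.95 to 0.99; systolic pressure SD 15 mmHg with ρ of 0.5 to 0.7; equal SD at both visits; no missing data.

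- Visit values: half-width H = 1.96 × SD × √(2/85). Weight: 1.96 × 16 × 0.1534 = 4.81 kg. Systolic: 1.96 × 15 × 0.1534 = 4.51 mmHg.
- Simple change: H × √(2(1 − ρ)).
- Baseline-adjusted (ANCOVA): H × √(1 − ρ²).

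| Variable | ρ | Visit values | Simple change | Baseline-adjusted |
|---|---|---|---|---|
| Weight, kg | 0.95 | 4.81 | 1.52 | 1.50 |
| Weight, kg | 0.98 | 4.81 | 0.96 | 0.96 |
| Weight, kg | 0.99 | 4.81 | 0.68 | 0.68 |
| Systolic, mmHg | 0.5 | 4.51 | 4.51 | 3.91 |
| Systolic, mmHg | 0.6 | 4.51 | 4.03 | 3.61 |
| Systolic, mmHg | 0.7 | 4.51 | 3.49 | 3.22 |

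The ratios between columns depend only on ρ. The half-widths scale with the SD: at 15 kg, weight gives 4.5 kg from visit values and 1.4 to 0.6 kg from simple change. Below ρ = 0.5, simple change is less precise than visit values (ratio 1.18 at ρ = 0.3); baseline adjustment never is, apart from the small cost of fitting one covariate.

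**4. What can still be read from the planned output**

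SAP Table 1 gives vital signs a Baseline window and windows for Weeks 2, 4, 8, 12 and 14. If the Baseline row is tabulated, subtracting it from a visit mean gives each arm's mean shift. If the same subjects contribute to both rows, that is the mean change itself. Its SD and confidence interval cannot be recovered, because the correlation is not reported. When visits are missed, the two rows also cover different subjects.

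**The case against.** **The SAP is silent rather than contrary.** Section 10.4.2 never says that it means visit values only. Section 10.3.2.1 opens with an almost identical sentence that also omits change, yet its heading is about change. SAP 3.0 presents the SAP as elaborating the protocol, so silence need not cancel the protocol's commitment. This stands to the extent that one can say the summary is not specified, and not that it was removed.

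**A reader might infer that shifts between arms could not be seen.** The documents do not support that. Means by visit and arm allow a crude shift to be read off, and Table 11, whose weight, blood pressure and pulse criteria involve change from baseline, is tabulated by arm.

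**A reader might infer that change will be reported only without a control.** That does not follow either. The two sequences in 10.1 and 10.4.3 keep the randomised arms distinguishable, with one on placebo until Week 14. If 10.4.3 includes Weeks 2 to 14, it shows controlled changes. The SAP does not say whether it does. It is in any case the long-term analysis, not the Week 14 one, and it gives no between-arm difference.

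**A reader might take the missing treatment difference as a broken promise.** It is not. The protocol promises descriptive summaries, and neither document promises ANCOVA for vital signs. Even for laboratory data the comparison covers selected parameters only.

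**The gain is uneven.** For blood pressure, simple change gains nothing at ρ = 0.5. This stands; the large gain is for weight.

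**It is late.** SAP 11.0 puts the Week 14 lock in February 2019, and the current SAP is dated August 2020. New wording cannot alter the locked analysis prospectively.

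**Conclusion.** The gap between protocol and SAP is real. It is a reporting weakness worth repairing, and it does not undermine the efficacy conclusions. As written, the main placebo-controlled vital-sign output is visit means without the SD of change or a between-arm difference. Modest shifts are therefore poorly estimated, above all in weight.

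Under the assumptions above, baseline adjustment narrows the weight half-width by a factor of about 3 to 7 (4.81 / 1.50 = 3.2; 4.81 / 0.68 = 7.1). For systolic pressure it narrows it by about 13% to 29% (1 − 3.91/4.51; 1 − 3.22/4.51), and simple change by 0% to 23% (1 − 3.49/4.51). The textual finding needs no assumption. The sizes depend on assumed correlations and, in absolute units, on assumed SDs.

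**What to change.** In SAP 10.4.2, specify for each Period 1 visit in Table 1, by arm, the layout already used in 10.4.3: n, baseline mean, visit mean, and the mean, SD and median of the change from baseline. Use subjects with both values at that visit. This meets the protocol's commitment.

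As an improvement beyond that commitment, add the upadacitinib-minus-placebo difference in change with a 95% CI, from a model with treatment and the baseline value, for weight, systolic and diastolic pressure, and pulse. No test is needed. State in 10.4.3 whether its by-visit tables include Weeks 2 to 14.

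The cost is one extra safety table and a few lines of SAP text; the data are already collected and windowed. The table can accompany the Week 104 safety analysis described in SAP 4.5. It must be labelled as added after the Week 14 database lock and unblinded analysis, so the between-arm estimates should be read as descriptive.

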10.4.3 Analysis of Long-Term Vital Sign

Analyses of mean change from baseline in continuous vital signs variables which are measured longitudinally will be performed by visits and by "as treated" treatment group sequences as described in Section 10.1. For each change from baseline analysis, the following summary statistics will be presented for each treatment group: sample size, baseline mean, visit mean, and the mean, standard deviation, and median of the changes from baseline.

Long-Term Vital Sign will also be summarized based on the number and percentage of subjects meeting the criteria for potentially clinical significant vital sign values for the Any Upadacitinib 15 mg QD group as described in Section 10.2.2. Similar baseline definition as described in Section 10.3.3.2 will be applied.

A listing of all subjects with any vital sign values meeting the criteria for potentially clinically significant vital signs will be provided. For each of these subjects, the whole course of the respective parameter will be listed.

11.0 Statistical Analysis to Account for the Impact of COVID-19 Pandemic

This section presents the changes in statistical analysis to handle the missing data due to COVID-19 and the additional data collected related to COVID-19. The Week 14 DBL was completed in Feb 2019. The Week 64 database lock was completed in Feb 2020. The analyses specified in this section applies to future database locks.

Patient Disposition

Reasons for premature discontinuation of study drug/study will be updated to add two additional reasons related to COVID-19:

- COVID-19 Infection
- COVID-19 Logistical restrictions

The number and percentage of subjects who prematurely discontinued from study drug/study due to COVID-19 infection or COVID-19 logistical restrictions will be summarized by randomized treatment group.

Summary of COVID-19 Impacted Visits

Types of missing visits related to COVID-19 will be collected for the protocol pre-specified visits. For each visit, the number and percentage of subjects impacted by COVID-19 will be summarized by the types of visit for each randomized treatment group as well as overall:

- In person, partial assessments done
- Virtual visit
- Missed visit

Efficacy Analyses

With respect to the COVID-19 pandemic, it would be reasonable to assume that missed visits and missing data due to self-quarantine or local government restrictions on travel or limitations on healthcare resources will impact subjects across treatment arms in a similar fashion and adopt the Missing at Random (MAR) assumption for missing data handling.

A sensitivity analysis will be conducted to handle this using AO data. MMRM will be used for continuous endpoints and GLMM defined in section 9.1.2 will be used for binary endpoints.

Safety Analyses

COVID-19 related AEs occurring on or after February 1, 2020 and COVID-19 related deaths occurred on or after February 1, 2020 will be collected.

Listings of subjects with AEs related to COVID-19 infection will be provided.

12.0 Version History

Table 12. SAP Version History Summary

Version	Date	Summary
1.0	12 Apr 2018	Original version
2.0	20 Dec 2018	Incorporated FDA's comment
3.0	20 August 2020	Incorporating updates 1) the study duration is extended for France, Belgium, Finland, Netherlands and Germany in protocol amendment 2.01, 2.02 and 2.03; 2) Add Week 104 data base lock (DBL) and final lock; 3) in statistical analysis related to COVID-19;4) add appendix G for low dose CT sub-study analysis plan 5) Update ASDAS Low Disease definition for Week 104 DBL 6) Include incident rate for all AESI for future DBL

